4.2 Scientific Rationale for Study Design

This study will evaluate the safety and tolerability of MK-1654 versus palivizumab and collect efficacy data to estimate the efficacy of MK-1654 relative to palivizumab in this population at increased risk for severe RSV, in accordance with the 2017 draft FDA Guidance for Industry: *Respiratory Syncytial Virus Infection: Developing Antiviral Drugs for Prophylaxis and Treatment* [Food and Drug Administration 2017].

This study will also assess the PK of MK-1654 at various time points up to 240 days after the first dose to observationally compare the PK data in this population to the PK of MK-1654 determined in the Phase 2b/3 pivotal efficacy study (MK-1654-004 [PN004] in healthy pre-term and full-term infants). In addition, MK-1654 PK will be assessed for up to 150 days after the RSV Season 2 dose.

Since the PK of palivizumab has been well studied and described in the literature, blood samples will not be collected from infants who are enrolled for 1 RSV season in the palivizumab group after the participant's treatment assignment is unblinded at the Day 60 visit in RSV Season 1. These eligible participants in the palivizumab group who will receive MK-1654 in RSV Season 2 will have PK, ADA, and SNA blood samples collected according to the SoA (see Section 1.3.1.3 SoA – RSV Season 1 Part 2 – Palivizumab Group).

4.2.1 Rationale for Endpoints

4.2.1.1 Efficacy Endpoints

Secondary and tertiary efficacy endpoints for this study are to estimate RSV-associated outpatient and inpatient MALRI (diagnosed as in [Table 1](#)) in RSV Seasons 1 and 2. The diagnostic criteria are based on published literature and information from clinical studies,

RSV expert panels, and WHO and CDC guidelines [Manoha, C., et al 2007] [Nair, H., et al 2010] [Simoes, E. A. F., et al 2015]. Cough or difficulty breathing are included based on the case definition for severe and very severe LRI by the expert panel on RSV vaccine development convened by the WHO [Simoes, E. A. F., et al 2015].

RSV-associated MALRI represents most of the RSV disease burden and is a clinically important and well-defined RSV disease endpoint across geographies and healthcare settings [Nair, H., et al 2010] that has been recommended by RSV prophylaxis trial expert committees [Simoes, E. A. F., et al 2015]. A secondary efficacy endpoint is the estimation of efficacy against RSV-associated MALRI from Day 1 through Day 150 postdose (the length of a typical RSV season in a temperate climate) in RSV Season 1. Assessment of efficacy against RSV-associated hospitalization from Day 1 through Day 150 postdose in RSV Season 1 is also planned as a secondary efficacy endpoint as this is an outcome of clinical importance to healthcare practitioners and healthcare systems.

Table 1 Respiratory Syncytial Virus (RSV)-associated Medically Attended Lower Respiratory Infection (MALRI) Diagnostic Criteria

Signs/Symptoms	Indicators of LRI/Severity	RSV
Endpoint definition requires at least 1 from each column seen in an outpatient or inpatient clinical setting (outpatient clinic, clinical study visit, Emergency Department, urgent care center, or hospital) and confirmed or observed by the investigator.		

 Cough Difficulty breathing 	
 Wheezing Chest wall in-drawing/Retractions Rales/Crackles Hypoxemia (SpO₂ <95% on room air at sea level, <92% on room air at altitude ≥1800 m, or 5 percentage points or more below baseline level in children with CLD or CHD with chronic underlying hypoxemia)^a Tachypnea (RR ≥60 breaths per minute for <2 months of age; ≥50 breaths per minute for 2 to 12 months of age; or ≥40 breaths per minute for >12 to 24 months of age) Dehydration due to respiratory symptoms 	
 RSV-positive RT-PCR NP sample (collected within 12 days of symptom onset or worsening)
CHD=congenital heart disease; CLD=chronic lung disease; LRI=lower respiratory infection; MALRI=medically attended lower respiratory infection; NP=nasopharyngeal; RR=Respiratory rate; RSV=respiratory syncytial virus; RT-PCR=reverse transcriptase-polymerase chain reaction; SpO ₂ =oxygen saturation as measured by pulse oximetry. ^a For severe MALRI: Severe hypoxemia (SpO ₂ <90% on room air at sea level; <87% on room air at altitude ≥1800 m) or the need for high flow nasal cannula, oxygen mask, or mechanical ventilatory support.		

In addition, RSV-associated MALRI and hospitalization through 180 days postdose in RSV Seasons 1 and 2 and RSV-associated severe MALRI through 150 days postdose in RSV Season 1 are planned as tertiary endpoints. The burden of RSV-associated hospitalizations is described in Section 2.2, and a decrease in hospitalization rate represents a benefit to public health.

An RSV expert panel convened for design of clinical endpoints for RSV prophylaxis studies in 2014 suggested that cough or difficulty breathing be a required component of the LRI clinical endpoint definition [Simoës, E. A. F., et al 2015]. This panel also proposed that the definition of LRI include the presence of lower chest wall in-drawing, or wheezing or crackles, or hypoxemia ($\text{SpO}_2 < 95\%$ on room air at sea level, $< 92\%$ on room air at altitude ≥ 1800 m, or 5 percentage points or more below baseline level in children with CLD or CHD with chronic underlying hypoxemia) in a child < 5 years of age with cough, tachypnea, or difficulty breathing. Typically, RSV infection starts with several days of mild upper respiratory tract signs, cough, and low-grade fever, followed by lower respiratory tract involvement and a worsening cough, with the infant becoming tachypneic and possibly having progressively more labored breathing, with dyspnea and retractions of the chest wall; crackles and wheezes are the most common auscultatory signs. Dehydration due to respiratory symptoms encompasses dehydration secondary to inability to feed.

The terms “difficulty breathing” or “labored breathing” are conventional in describing the signs and symptoms of pediatric RSV in the published literature; several recent active surveillance studies have reported a high frequency of difficult or labored breathing in infants and young children with RSV. Among hospitalized infants, it was reported that 81%, 75%, and 73% of infants aged 0 to 2 months, 3 to 5 months, and 6 to 11 months had difficulty breathing on admission [Rha, B., et al 2018]. A CDC active surveillance study in children < 5 years of age with RSV found that 73%, 85%, and 95% of children presenting to the pediatrician’s office, Emergency Department, and hospital for admission, respectively, had labored breathing [Hall, C. B., et al 2013]. Clinical signs of difficulty breathing or labored breathing may include tachypnea, grunting, nasal flaring, retractions, cyanosis, and/or apnea.

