3 HYPOTHESES, OBJECTIVES, AND ENDPOINTS

This is an estimation study without hypotheses. The following objectives will be evaluated in the study population. The RSV Season 1 42-day safety follow-up period consists of safety data collected from Day 1 post Dose 1 through 14 days post Dose 2.

Primary Objectives	Primary Endpoints

 RSV Season 1: To evaluate the safety and tolerability of MK-1654 compared to palivizumab in RSV Season 1 as assessed by the proportion of participants experiencing AEs. 	
 Solicited injection-site AEs from Days 1 through 5 after each dose Solicited daily body temperature, with fever defined as rectal temperature $\geq 102.2^{\circ}\text{F}$ ($\geq 39.0^{\circ}\text{C}$) or axillary temperature $\geq 101.7^{\circ}\text{F}$ ($\geq 38.7^{\circ}\text{C}$) from Days 1 through 5 after each dose Solicited systemic AEs from Days 1 through 5 after each dose Anaphylaxis/hypersensitivity AESI from Days 1 through 42 post Dose 1 Rash AESI from Days 1 through 42 post Dose 1 Nonserious AEs from Days 1 through 42 post Dose 1 and 14 days after each subsequent dose SAEs through the duration of participation in RSV Season 1
Secondary Objectives	Secondary Endpoints

 RSV Season 1: To estimate the efficacy of MK-1654 compared to palivizumab as assessed by the incidence of RSV-associated MALRI (outpatient and inpatient) from Days 1 through 150 post Dose 1 in RSV Season 1. 	
 RSV-associated MALRI (outpatient and inpatient), defined as the following seen in an outpatient or inpatient clinical setting: 
 Cough or difficulty breathing; AND 
 1 or more of the following: wheezing, chest wall in-drawing/retractions, rales/crackles, hypoxemia, tachypnea, dehydration due to respiratory symptoms; AND 
 RSV-positive RT-PCR NP sample

 • RSV Season 1: To estimate the incidence of RSV-associated hospitalizations from Days 1 through 150 post Dose 1 in RSV Season 1 in the MK-1654 and palivizumab groups. 	
 • RSV-associated hospitalization, defined as the following: 
 ▪ Hospital admission for respiratory illness; AND 
 ▪ RSV-positive RT-PCR NP sample

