9.6.1 Statistical Methods for Efficacy Analyses

To estimate the efficacy of MK-1654 compared to palivizumab against RSV-associated MALRI through Day 150 post Dose 1 in RSV Season 1, efficacy is defined as:

$$E\% = 100 * \{1 - (R_t/R_p)\}$$

Where R_t and R_p are the incidence rates of RSV-associated MALRI in the MK-1654 and palivizumab groups, respectively. The incidence rate R_t is defined as $R_t = C_t/T_t$, where C_t = the count of RSV-associated MALRI cases in the MK-1654 group and T_t = total person-time of follow-up for efficacy in the MK-1654 group. The incidence rate R_p is defined similarly.

A modified Poisson regression approach with robust variance [Zou, G. 2004] will be used for the efficacy analyses. The mean and 95% CI of relative risk, R_t/R_p , will be obtained from the model, and will be used to estimate the mean and 95% CI of E. The modified Poisson regression model will include treatment group, and stratification variables of region (Southern Hemisphere and Northern Hemisphere) and participant condition (CLD, CHD, neither CLD nor CHD ≥ 29 weeks gestational age, and neither CLD nor CHD < 29 weeks gestational age) as covariates. If the number of participants in any stratum is too small and/or convergence cannot be achieved, the covariate may be excluded from the model. To allow for differences in follow-up times among the participants, the log of the follow-up time as the offset term will be added in the modified Poisson regression.

The incidence of RSV-associated hospitalization occurring from Days 1 through 150 post Dose 1 in the MK-1654 and palivizumab groups in RSV Season 1 will be estimated and the exact 95% CIs will be provided using the Chi-square distribution for Poisson variable method [Ulm, K. 1990].

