An additional analysis to estimate the efficacy of MK-1654 compared to palivizumab against RSV-associated MALRI from Day 1 through the end of the first RSV season will be performed. In this analysis, only infants who develop RSV-associated MALRI from Day 1 through the end of their RSV season will be defined as cases. In other words, the efficacy follow-up duration to be included in the analysis will be until either the date of the end of the RSV season or the Day 150 date, whichever occurs first, thereby only including the relevant period of risk of RSV disease for each infant. A similar analysis will be performed for the endpoint of RSV-associated hospitalization and the incidence of this endpoint along with the CI will be estimated for each treatment group. The key efficacy analyses for secondary endpoints are summarized in [Table 6](#).

For the efficacy analyses, cases of both RSV A and RSV B associated MALRI (or hospitalization) will be counted as endpoints. The efficacy of MK-1654 relative to palivizumab in RSV Season 1 against RSV A associated MALRI and RSV B associated MALRI will also be estimated separately. Similarly, the incidence of RSV A associated hospitalization and RSV B associated hospitalization in each treatment group will be estimated separately.

The incidence of RSV-associated MALRI and RSV-associated hospitalization through Day 180 postdose MK-1654 in RSV Season 2 and the corresponding 95% CIs will be computed:

- Separately by treatment group to which participants were randomized to in RSV Season 1, and
- Both treatment groups combined.

Table 6 Analysis Strategy for Key Efficacy Variables

Endpoint/Variable (Description, Time Point)	Primary vs. Supportive Approach	Statistical Method ^a	Analysis Population	Missing Data Approach
Secondary Endpoints				
Incidence of RSV-associated outpatient and inpatient MALRI from Day 1 through Day 150 post Dose 1 in RSV Season 1	P/S	Modified Poisson regression (estimate, 95% CI)	FAS/PPE	Missing data will not be imputed
Incidence of RSV-associated hospitalization from Day 1 through Day 150 post Dose 1 in RSV Season 1	P/S	Exact 95% CIs using the Chi-square distribution for Poisson variable (estimate, 95% CI)	FAS/PPE	Missing data will not be imputed
Incidence of RSV-associated outpatient and inpatient MALRI from Day 1 through the end of RSV Season 1	S	Modified Poisson regression (estimate, 95% CI)	PPE	Missing data will not be imputed

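### Section 4.2.1.1 plans to assess efficacy against RSV hospitalization, but the objective, Section 9.6.1 and Table 6 give only separate per-arm incidences, so no between-arm estimate is prespecified for this key secondary endpoint.

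*Combined protocol and SAP*

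**What the plan says.** The combined protocol and SAP describes the Day 1-150 hospitalization endpoint in two ways.

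- **As efficacy.** The endpoint rationale in Section 4.2.1.1 has "Assessment of efficacy against RSV-associated hospitalization from Day 1 through Day 150 postdose in RSV Season 1", which "is also planned as a secondary efficacy endpoint as this is an outcome of clinical importance to healthcare practitioners and healthcare systems". Section 4.2 frames the efficacy aim as relative to palivizumab, and Section 2.3 anticipates better protection than palivizumab against both MALRI and hospitalization.
- **As incidence by group.** The secondary objective in Section 3 is "To estimate the incidence of RSV-associated hospitalizations from Days 1 through 150 post Dose 1 in RSV Season 1", in the two groups. Section 9.6.1 says that this incidence "will be estimated and the exact 95% CIs will be provided using the Chi-square distribution for Poisson variable method". For the supportive analysis to the end of the season, "the incidence of this endpoint along with the CI will be estimated for each treatment group". The RSV A and RSV B hospitalization analyses are also by group. Table 6 repeats the per-arm method for FAS and PPE.

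MALRI is treated differently. Its objective is efficacy compared with palivizumab, and the relative risk and its interval "will be obtained from the model, and will be used to estimate the mean and 95% CI of E".

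Section 9.1 lists hospitalization among the key secondary endpoints. Section 9.3 states that there is no formal hypothesis testing. Section 9.6 allows nominal p-values for efficacy analyses but defines no hospitalization comparison to which one could belong.

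**The concern.** In a randomized trial against an active control, efficacy against an outcome means a contrast between arms. For hospitalization the plan promises that in one place and omits it everywhere the analysis is defined. The report would then carry two intervals, and any comparison would be either informal or chosen after the results are known.

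Overlap of two separate 95% intervals is not a valid comparison. It can coexist with a ratio interval that excludes 1. It also fails to show how large a disadvantage of MK-1654 remains compatible with the data. Both matter for an endpoint that the protocol itself calls clinically important.

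**Working it through.** **1. Inputs from the documents.** 500 participants per arm, 1:1; 10% attrition, so 500 × 0.9 = 450 per arm; MALRI incidence 15% without prophylaxis; expected MALRI efficacy versus palivizumab 25% to 40% (Section 9.9.1). No hospitalization rate is given, and Table 8 covers MALRI only.

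**2. Reproducing the plan's figures.** The exact Poisson interval for x events is χ²(0.025; 2x)/2 to χ²(0.975; 2x+2)/2, divided by n. With n = 450:

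| Incidence | x | Computed | Table 8 |
|---|---|---|---|
| 0.045 | 20.25 | 0.0276-0.0693 | 0.028-0.069 |
| 0.06 | 27 | 0.0395-0.0873 | 0.040-0.087 |
| 0.075 | 33.75 | 0.0519-0.1049 | 0.052-0.105 |

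All six distinct per-arm intervals in Table 8 match. The relative efficacy intervals match within simulation noise; for 40% efficacy the mean simulated limits are (-5.6, 64.2), against (-4.6, 64.5) stated. The per-arm method is therefore understood as the plan intends it.

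**3. Per-arm intervals for hospitalization, assumed counts, n = 500.**

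- 12 events: limits 6.20 and 20.96 events, or 1.24% to 4.19%.
- 25 events: limits 16.18 and 36.91 events, or 3.24% to 7.38%.

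The two intervals overlap between 3.24% and 4.19%.

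**4. Comparative interval from the same data.** Given the total number of events, the MK-1654 count is binomial with probability π. The rate ratio is [π/(1-π)] × (T_p/T_t), where T_p and T_t are person-time on palivizumab and MK-1654. Put the Clopper-Pearson limits for π into this formula. With equal person-time, 12 of 37 events gives π limits 0.1801 and 0.4979. The ratio is 12/25 = 0.48, with limits 0.1801/0.8199 = 0.22 and 0.4979/0.5021 = 0.99.

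**5. Range of assumed counts, 500 per arm, equal person-time.**

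| MK-1654 vs palivizumab | Palivizumab rate | Ratio | Exact 95% CI |
|---|---|---|---|
| 3 vs 5 | 1% | 0.60 | 0.09-3.08 |
| 6 vs 10 | 2% | 0.60 | 0.18-1.82 |
| 9 vs 15 | 3% | 0.60 | 0.23-1.46 |
| 15 vs 25 | 5% | 0.60 | 0.29-1.18 |
| 12 vs 25 | 5% | 0.48 | 0.22-0.99 |

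The 12 versus 25 row shows that overlapping per-arm intervals can hide a ratio interval that excludes 1. The rows at 0.60 show the more likely outcome if the effect resembles that expected for MALRI: a wide interval that includes 1.

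**The case against.** The strongest reply is that the omission is deliberate. The objective asks for incidence by group, and the analysis delivers exactly that. The split between efficacy for MALRI and incidence for hospitalization runs consistently through the objectives, the SAP summary, the methods and Table 6. Only the rationale in Section 4.2.1.1 names efficacy against hospitalization as a planned assessment, and rewording it would remove the contradiction. Precision would also be poor. At a 3:5 ratio of events, the exact interval first excludes 1 at 27 versus 45 events. That is 45/500 = 9% hospitalized on palivizumab, above the highest palivizumab incidence for all MALRI in Table 8 (0.0825). Finally, a reader can form a crude ratio from the reported rates, and inpatient cases that meet the MALRI definition already enter the MALRI estimate.

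Much of this stands. The objective and its analysis agree, so the conflict is between Section 4.2.1.1 on one side and the objective and SAP on the other. A ratio would probably not reveal a difference if the true reduction is 25% to 40%.

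It does not dispose of the point. Small counts are not a bar elsewhere in the plan: Section 9.6.1 estimates relative efficacy separately for RSV A and RSV B MALRI, and Section 9.6.2 gives between-arm 95% CIs for adverse events at 1% incidence in one group, about 5 of 500. The absence of hypothesis testing is no bar either, since the MALRI ratio is itself estimation. Neither a crude ratio worked out by the reader nor a MALRI estimate that includes inpatient cases is a prespecified hospitalization contrast with an interval.

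**Conclusion.** The point holds as an inconsistency with a practical consequence: the plan calls hospitalization an efficacy endpoint and prespecifies no between-arm estimate for it. The consequence depends on the counts. At 12 versus 25 the planned intervals overlap while the ratio is 0.48 (0.22 to 0.99). At 15 versus 25 the ratio is 0.60 (0.29 to 1.18), and its value lies in stating the uncertainty. These figures rest on assumed counts, 500 per arm and equal person-time.

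Three stronger readings are tempting but unsupported.

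- A reader might infer that the trial's most important outcome goes unanalysed. The documents do not rank it so: the primary endpoints are safety, MALRI is the first secondary efficacy endpoint, and hospitalization is described only as clinically important.
- A reader might infer that per-arm reporting will conceal a real difference. Within the 25% to 40% efficacy expected for MALRI, the ratio interval would usually include 1 as well.
- A reader might infer the same contradiction for severe MALRI. That endpoint is tertiary, its objective is incidence by group, and Section 4.2.1.1 promises no efficacy assessment for it.

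**What to change.** In Section 9.6.1 and Table 6, keep the per-arm incidence. Add a descriptive hospitalization rate ratio for Days 1-150, with efficacy as 1 minus the ratio and an exact conditional 95% CI based on person-time, in FAS and PPE. Label it as estimation with low expected precision. Align the hospitalization objective in Section 3 and the synopsis with Section 4.2.1.1.

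Rewording Section 4.2.1.1 to speak of incidence would resolve the inconsistency, but it would leave the trial without a prespecified comparison on this endpoint. A ratio for severe MALRI is optional.

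The cost is a short addition to the text and one extra row per table. The interval will be wide and should be shown as such. No additional data, participants or multiplicity adjustment are needed.
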